Eligible participants will be randomised to receive either 7-day atorvastatin 20mg (25 participants), or 7-day placebo (25 participants) administration. Randomisation will occur on the day of screening, or up to a maximum of 4 weeks after screening. Randomisation after the Screening Visit will occur in the event that further information is needed before determining whether participants are eligible to take part (for example, if a participant needs to follow-up with details of allergies, or previous studies they have taken part in). In this case, if more than 4 weeks have elapsed, another Screening Visit will be performed to ensure participants are still eligible. The randomisation code will be drawn up by a researcher not involved in the study using an online randomisation tool (<https://www.sealedenvelope.com/simple-randomiser/v1/lists>). Randomised participants will be given 7 days of the drug to take home, as well as full instructions of how and when to take them.

The atorvastatin drug and the placebo will be provided by the Oxford Pharmacy Stores and will be encapsulated at the Neurosciences Building according to previously agreed standard operating procedures (APPENDIX G: Neurosciences, SOP Number: Encapsulation Version 2: 22.10.2012). Blinding will be achieved by the identical matching of the atorvastatin and placebo treatments. Participants will not be aware of the treatment that they will be receiving; neither will the researcher, as this study is double-blind.

Allocation of treatments will be recorded on a Randomisation List, which will be updated when each new participant enters the randomised phase. The list will be held at the Neurosciences Building by a scientist uninvolved in the study.

The study medication and placebo will be stored in a secure environment at the Neurosciences Building accessible only to staff. It will be stored at room temperature and accounted for using agreed study documentation. Using the Randomisation List and the participant's unique randomisation code, staff will determine whether to dispense active or placebo tablets.

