The randomisation code will be broken if a participant requires treatment for a new medical condition or experiences serious adverse reactions and either of these situations make it clinically important to know what medication they are taking. A 24/7 emergency mobile contact number will be provided on a wallet-sized card given to participants during their Research Visit. The research team member on-call will be able to contact the medical supervisor and they will make the decision to unblind. In order to unblind the participant, the medic will access the list kept in a secure cabinet at the Neurosciences Building and will disclose the allocation within a maximum of one hour. If breaking the code is necessary, only the individual's code will be broken. Data from unblinded participants will not be admitted to analysis. If unblinding occurs, the researcher will record the reason and result of the unblinding, as well as the date and time of the event.

During the week of drug/placebo administration, participants will be advised not to drink alcohol and not to carry out activities requiring full alertness, such as driving, if they are aware of any impairment. During this week, a researcher will phone up the participant on day 2 and day 4 to check that there are no concerns. Additionally,

participants will receive a text message every day reminding them to take the study medication. They will have the 24-hour contact phone number of a member of the study team and be encouraged to get in contact if they have any concerns or queries during the study week, or if their medication or health status changes.

Subsequent Visits

The Research Visit (approximately 2 hours) will take place after day 7 of atorvastatin/placebo administration. This visit will involve administration of behavioural tasks measuring emotional and reward processing. It will take place at the Neurosciences Building, Warneford Hospital.

Participants will complete the following questionnaires before the behavioural tasks:

- Positive and Negative Affect Schedule (PANAS)
- Side-effects questionnaire
- State Anxiety Inventory (state-STAI)
- Visual Analogue Scales (VAS)

Also, phlebotomy will be repeated to obtain a sample of:

- high sensitivity-C Reactive Protein

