The behavioural tasks will include the Oxford Emotional Test Battery (ETB), which has previously been found to be sensitive to the effects of antidepressants, and a reward task of Probabilistic Instrumental Learning (PIL). The ETB involves the presentation of emotion-related words and pictures of faces with different expressions. The reward task involves repeatedly choosing between two options and there is the possibility of winning up to £10 depending on the choices made (see 'Expenses and Benefits' below). All stimuli will be presented on a computer screen and participants will be required to respond via button presses on a keyboard.

Participants will be asked to report their adherence to the 7-day administration of atorvastatin/placebo.

At the end of the research visit, a member of the study team will ask participants to try to guess which treatment they received, as a measure of how successful the blinding was.

Sample Handling

Blood samples (4mL = i.e. 1 teaspoon) taken during the Screening Visit and the Research Visit for investigating hs-CRP will be handled at the Neurosciences Building's laboratory. On the same day, they will be rendered acellular by centrifugation on receipt and stored at -30°C until assay. Any excess material remaining at the end of the study will be disposed of by the laboratory within 6 months according to the Human Tissue Authority guidelines. The samples will be stored in a freezer at the Neurosciences Building in an anonymised form. Access to the samples will be by the research team and the samples will be in the custody of [name] who will hold the key code linking the samples to a particular individual. The samples will be analysed for once all participants have completed the study.

Female participants will be required to give a urine sample for a pregnancy test at the Screening Visit. Urine samples will be destroyed immediately after the test result has been obtained.

Discontinuation/Withdrawal of Participants from Study

Each participant has the right to withdraw from the study at any time. In addition, the Investigator may discontinue a participant from the study at any time if the Investigator considers it necessary for any reason including:

- Pregnancy

- Ineligibility (either arising during the study or retrospectively having been overlooked at screening)
- Significant protocol deviation
- Significant non-compliance with treatment regimen or study requirements
- Withdrawal of Informed Consent

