- Loss to follow up

If a participant is withdrawn, no further procedures or observations will continue to be required. Withdrawal from the study will result in exclusion of the data for that participant from the analysis. Withdrawn participants will be replaced. The reason for withdrawal, if given, will be recorded in the Participant Log of the Research Master File.

Definition of End of Study

The end of the study for participant involvement is the date of the last visit of the final participant.

Expenses and Benefits

Participants will be paid £100 upon completion of their participation in the research. In addition, they may win up to £10 depending on the choices they make in the reward task (see 'Subsequent Visits' above). If they do not complete the study, they will be given a pro-rata amount to recompense the time they did spend in the study. Reasonable travel expenses for any visits will be reimbursed on production of receipts, or a mileage allowance provided as appropriate.

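### Participants with complete Research Visit data can be dropped after randomisation through withdrawal or unblinding, and no planned analysis keeps them in their assigned group

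*Combined protocol and SAP*

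**What the plan says.** Three places set the exclusion.

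- Section 6, Discontinuation/Withdrawal: "Withdrawal from the study will result in exclusion of the data for that participant from the analysis. Withdrawn participants will be replaced". Section 9, Analysis of Outcome Measures, repeats the exclusion.
- Section 6, on breaking the code: "Data from unblinded participants will not be admitted to analysis". The triggers are a new medical condition needing treatment, or a serious adverse reaction, where it is clinically important to know the treatment.
- Section 8(d) adds that a participant whose code is broken is advised to stop the medication and is withdrawn.

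The investigator may discontinue a participant at any time for any reason considered necessary. The listed reasons include significant protocol deviation, ineligibility discovered in retrospect, and "Significant non-compliance with treatment regimen or study requirements". Under the Research Visit, section 6 states: "Participants will be asked to report their adherence to the 7-day administration of atorvastatin/placebo". That visit also yields the emotional and reward tasks, the post-dose questionnaires and the second hs-CRP sample.

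After withdrawal, "If a participant is withdrawn, no further procedures or observations will continue to be required". Reasons are logged, but the documents do not commit to reporting them by arm. Section 9 names t-tests and ANOVA; it defines no as-randomised set and no sensitivity analysis.

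**The concern.** Randomisation protects the comparison only while the people analysed are those randomised, or a subset chosen without regard to anything treatment could have changed. Non-compliance, protocol deviation and unblinding all happen after randomisation, and side-effects may contribute to each. Adherence is reported at the same visit as the outcomes, so a participant can supply complete data and then be excluded. No threshold is given for what counts as significant non-compliance.

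Replacement restores 25 per group but does not undo any selection, and a final table showing 25 v 25 would not reveal that anyone had been removed. At stake is whether a reader could tell if the drug-placebo difference depends on who was kept.

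**Working it through.** **The plan's own figure.** Section 9 gives drug mean 10.64 (SD 9.77), placebo mean 3.36 (SD 5.96), 25 per group and power 0.9. Significance level and sidedness are not stated; I assume two-sided 5%.

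- Difference: 10.64 − 3.36 = 7.28.
- Planning SD: √[(9.77² + 5.96²)/2] = √65.49 = 8.09. Standardised difference: 7.28/8.09 = 0.90.
- Noncentrality: 7.28/(8.09 × √(2/25)) = 3.18. Normal approximation: Φ(3.18 − 1.96) = 0.889. Noncentral t on 48 df: 0.876.

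The stated 0.9 is reproduced to within rounding. It refers to 25 analysed per group, which replacement maintains, so the exclusion rule does not make it wrong.

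**Size of the possible bias.** The documents give no exclusion rate, so these inputs are assumptions: a net k drug-arm completers are removed and replaced (25 + k randomised to drug, 25 v 25 analysed), and they differ by δ = 0.5 or 1.0 SD.

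- (A) δ measured from those retained: bias = δ × k/(25 + k).
- (B) δ measured from the mean of all randomised: bias = δ × k/25.

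The rejection rate under a true null is the noncentral t probability on 48 df with noncentrality bias × √12.5.

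| k removed | (A) bias, SD | (A) bias, points | (A) null rejection | (B) null rejection |
|---|---|---|---|---|
| 1 of 26 | 0.02 to 0.04 | 0.16 to 0.31 | 5.1% to 5.2% | 5.1% to 5.2% |
| 2 of 27 | 0.04 to 0.07 | 0.30 to 0.60 | 5.2% to 5.8% | 5.2% to 5.9% |
| 5 of 30 (extreme) | 0.08 to 0.17 | 0.67 to 1.35 | 6.0% to 8.9% | 6.4% to 10.7% |

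Example, k = 2 and δ = 1.0 under (A): 2/27 = 0.074 SD; 0.074 × 8.09 = 0.60 points; noncentrality 0.074 × √12.5 = 0.26; rejection 5.8%. Equal removal from both arms with equal δ gives zero bias and 5.0%.

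The last row needs five net removals from one arm, all of them completers, in a seven-day study. Section 4 describes the other common side-effects as under 1/10 and usually mild, so the upper rows are the more plausible.

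**Cost of keeping the data.** Worst case: k participants kept on drug show no drug effect at all and are also replaced, giving 25 + k v 25. The difference becomes 7.28 × 25/(25 + k).

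- k = 1: 7.00, power 0.857.
- k = 2: 6.74, power 0.837. If the mixture also widens the drug-arm SD, its variance becomes 9.77² + (2/27)(25/27) × 7.28² = 99.1, the planning SD 8.20 and the power 0.83.
- k = 5 (extreme): 6.07, power 0.776.

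**The case against.** The strongest reply is that few people are affected. Tasks are done only after day 7 and procedures stop on withdrawal, so early leavers have nothing to retain. This stands: for them the issue is missing data, and the added analysis remains complete-case. Exclusion for a characteristic that predates randomisation, judged blind, such as earlier use of the same tasks, need not bias anything. That stands too.

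It may also be said that the withdrawal wording is aimed at people who stop before finishing. That is a natural reading, but the rules carry no such limit, and retrospective ineligibility is a listed reason that can arise after completion. Removal of a completer is permitted, not certain.

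Blinding helps. On allocation, "neither will the researcher, as this study is double-blind"; on hs-CRP, "The samples will be analysed for once all participants have completed the study". Neither known allocation nor hs-CRP results should therefore drive a withdrawal, though a broken code is a partial exception. What remains open is selection through side-effects and adherence, which can differ by arm under full blinding.

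A reader might infer that the side-effects comparison suffers most, because anyone unblinded for a serious adverse reaction is removed by rule. The documents do not support that. Under section 8(d) such a participant is withdrawn, so unblinding during the dosing week would usually leave no post-dose questionnaire to recover; only unblinding after the visit removes collected data.

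Finally, the study is exploratory and uses the drug as a pharmacological tool (sections 2 and 4), so an on-treatment contrast suits its aim. I agree, and the planned set can stay.

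**Conclusion.** The concern holds for randomised participants who have Research Visit data and are then withdrawn or unblinded. The plan allows their removal for post-randomisation reasons and includes no analysis that would show the effect.

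The likely bias is small, of unknown direction, and zero if removals are unrelated to arm or outcome. With an assumed net one or two removals at 0.5 to 1.0 SD, the null rejection rate is about 5.1% to 5.9%; the 6.0% to 10.7% range for five removals is an extreme case. These figures rest on assumed counts and differences, because the documents give neither.

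A reader might go further and infer that the main comparison is invalid or the study underpowered. Neither follows: the stated power reproduces at 25 analysed per group, and nothing in the documents shows that such removals will occur. This is an inexpensive gap worth closing, not an error in the sample size.

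**What to change.** - Amend the two rules in section 6 and the sentence in section 9 so that data already collected from randomised participants are kept, unless the participant withdraws consent to their use. Check the wording against the information sheet and consent form, which are not in the documents reviewed.
- Pre-specify an analysis of every randomised participant with usable outcome data, in the assigned group, including the side-effects questionnaire. Report it beside the planned set, which may stay as the on-treatment contrast. Define usable in advance; it may leave out participants found ineligible on a pre-randomisation characteristic, judged blind.
- State that replacements may be recruited but do not displace the original participant.
- Report withdrawals, unblindings, missing Research Visits and their reasons by arm. These counts show how much is missing for early leavers.

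The change should be made before the randomisation code is opened for analysis. It costs protocol wording, one extra analysis run and a by-arm flow table, with no extra visits. The downside is dilution in the added analysis only: worst-case power of about 0.86 with one such participant kept or 0.84 with two, while the on-treatment analysis stays at 0.88. Clinical decisions to unblind or stop treatment are unchanged.

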7. INTERVENTION(S)

a) Drug/Substance 1

Name of drug/substance to be used	Atorvastatin
Formulation and route of administration for study	20mg atorvastatin tablets will be encapsulated in opaque capsules
Dose and route of administration for study	20mg atorvastatin once daily at night-time, oral dose
Duration of treatment for study	7 days
Licence status of this drug/substance	Atorvastatin is a licensed drug
Usual Indication	Atorvastatin is usually indicated in adult patients with primary hypercholesterolaemia, or combined (mixed) hyperlipidaemia in adult patients who have not responded adequately to diet and other appropriate measures, in adult patients with homozygous familial who have not responded adequately to diet and other appropriate measures, and in adult patients with atherosclerotic cardiovascular disease or diabetes mellitus for prevention of cardiovascular events
Usual Dose	10-80mg once daily, at night-time

Usual duration of treatment	Life-long
Where will drug/substance be sourced from?	Oxford Pharmacy Stores
Where will drug/substance be stored?	Atorvastatin will be stored within the Neurosciences Building, Warneford Hospital. It will be stored at room temperature in a locked cupboard, which is suitable for drug storage.
How will drug/substance be dispensed?	Atorvastatin will be dispensed from the Neurosciences Building, Warneford Hospital by a study medic or nurse.
How will the drug/substance be prepared by the researchers for use in this study?	Atorvastatin will be encapsulated by trained clinical trial support staff using our Standard Operating Procedure (APPENDIX G: ENCAPSULATION STANDARD OPERATING PROCEDURE).

b) Drug/Substance 2 (or placebo)

Name of drug/substance to be used	Lactose Placebo
Formulation and route of administration for study	Placebo tablets will be encapsulated in opaque capsules
Dose and route of administration for study	One capsule once daily at night-time, oral dose
Duration of treatment for study	7 days
Licence status of this drug/substance	N/A
Usual Indication	N/A
Usual Dose	N/A
Usual duration of treatment	N/A
Where will drug/substance be sourced from?	Placebo tablets will be sourced from HSC (www.hsconline.co.uk).
Where will drug/substance be stored?	Placebo will be stored within the Neurosciences Building, Warneford Hospital. It will be stored at room temperature in a locked cupboard, which is suitable for drug storage.
How will drug/substance be dispensed?	Placebo will be dispensed from the Neurosciences Building, Warneford Hospital by a study medic or nurse.
How will the drug/substance be prepared by the researchers for use in this study?	Placebo will be encapsulated by trained clinical trial support staff using our Standard Operating Procedure (APPENDIX G: ENCAPSULATION STANDARD OPERATING PROCEDURE).

8. SAFETY

a) Definitions

Adverse Event (AE)	Any untoward medical occurrence in a participant to whom a substance has been administered, including occurrences which are not necessarily caused by or related to that substance.
Adverse Reaction (AR)	An untoward and unintended response in a participant to a substance, which is related to any dose administered to that participant. A causal relationship between the administered substance and an AE is at least a reasonable possibility, i.e. the relationship cannot be ruled out. All cases judged by either the reporting medically qualified professional or the Sponsor as having a reasonable suspected causal relationship to the study intervention qualify as adverse reactions.
Serious Adverse Event (SAE)	A serious adverse event is any untoward medical occurrence that: 
 • results in death • is life-threatening • requires inpatient hospitalisation or prolongation of existing hospitalisation • results in persistent or significant disability/incapacity • consists of a congenital anomaly or birth defect. 
Other ‘important medical events’ may also be considered serious if they jeopardise the participant or require an intervention to prevent one of the above consequences.
 
NOTE: The term "life-threatening" in the definition of "serious" refers to an event in which the participant was at risk of death at the time of the event; it does not refer to an event which hypothetically might have caused death if it were more severe.

Serious Adverse Reaction (SAR)	An adverse event that is both serious and, in the opinion of the reporting Investigator, believed with reasonable probability to be due to one of the study treatments, based on the information provided.
Suspected Unexpected Serious Adverse Reaction (SUSAR)	A serious adverse reaction, the nature and severity of which is not consistent with the information about the medicinal product set out in its summary of product characteristics (SmPC).

b) Reporting Procedures for Serious Adverse Events or Reactions

A serious adverse event (SAE) occurring to a participant should be reported to CTRG and the Medical Sciences IDREC where, in the opinion of the Principal Investigator, the event was ‘related’ (resulted from administration of any of the research procedures) and ‘unexpected’ (the type of event is not listed in the protocol as an expected occurrence). Reports of related and unexpected SAEs should be submitted within 15 days of the Principal Investigator becoming aware of the event. For fatal and life-threatening SUSARs, this will be done no later than 7

calendar days after the Sponsor or delegate is first aware of the reaction. Any additional relevant information will be reported within 8 calendar days of the initial report.

c) Safety of Participants

What level of baseline screening will take place for this study?

All participants will undergo a Screening Visit to ensure only eligible participants take part. The following will be recorded at baseline screening:

- Demographic information (age [years, months], years in full-time education)
- Number of cigarettes smoked per day, units of alcohol consumed per week, caffeinated drinks consumed per day
- Current and prior use of drugs (to exclude for drug use in the three months prior to the study)
- SCID-5 interview (Structured Clinical Interview for DSM-5) to probe for current or past psychiatric illness
- Beck Depression Inventory (BDI)
- Eysenck Personality Questionnaire (EPQ)
- State and Trait Anxiety Inventory (STAI)
- Positive and Negative Affect Schedule (PANAS)
- Snaith-Hamilton Pleasure Scale (SHAPS)
- Side-effects questionnaire
- Visual Analogue scales (VAS)

To ensure it is safe to administer the drug to the participant, the following will be recorded:

- Weight, height, and BMI
- Medical history (including family psychiatric history)
- Details of current and past medication
- Urine pregnancy test (female participants only)

Also, phlebotomy will be undertaken to obtain a sample of:

- high sensitivity-C Reactive Protein

Participation in prior studies will be recorded to exclude for individuals who have used the same/similar emotional processing tasks.

Provide details about the safety monitoring of participants and the staff/researchers carrying this out

During the week of drug/placebo administration, participants will be advised not to drink alcohol and not to carry out activities requiring full alertness if they are aware of any impairment. During the week of drug/placebo administration, a researcher will phone up the participant on day 2 and day 4 to check that there are no concerns. Participants will have the 24-hour contact phone number of a member of the study team and be encouraged to get in contact if they have any concerns or queries during the study week, or if their health status changes. The named researcher will in turn contact a qualified medical doctor if necessary.

Give details on the medical cover required and who will provide this cover	
A medical doctor who is part of the research team will review the screening and make a final judgment about including participants in the study. A qualified medical doctor will be contacted if a participant expresses concern to a named researcher regarding side-effects or health status changes during the study week.	
Will the participants' GP be informed about their participation in the study? If not, please justify	
Participants' GPs will not be informed about their participation in the study. Seven days of atorvastatin 20mg administration is not regarded as a clinically significant intervention and is not expected to have any impact on participants' health or wellbeing. We are excluding participants who are pregnant, breastfeeding, women of child-bearing potential not using appropriate contraceptive measures, or people who have any medical conditions for whom the study would not be suitable.	
What is your planned procedure if an incidental finding is suspected?	
Participants will be screened to exclude those with past or current psychiatric symptoms and Best Practice Guidance (BPG) 08 (Psychological distress) will be followed in order to ensure best practice in situations where participants with psychological distress are identified. The guidance in this document around confidentiality and researcher's training will also be adhered to.	
If an incidental finding has clinical implications, what action will you take?	
If a researcher has concerns that a volunteer may have an undiagnosed psychiatric condition that is causing distress (identified during the Screening Visit or following review of the mood-related questionnaires), CUREC guidance (BPG08) will be followed. The researcher will seek advice from the Principal Investigator who may discuss the symptoms in greater detail with the volunteer and/or offer the opportunity to speak with a senior clinical researcher. If the volunteer indicates that they are not currently receiving support and it is felt necessary, they will be encouraged to contact their GP.	
Please give details of departmental SOPs (if any) that will be followed in the case of an incidental finding	
As above.	

d) Ethical Considerations

Will you include any vulnerable participants (e.g. children, elderly)? If yes, please describe how they are defined as vulnerable and detail any CUREC approved procedures or guidance that you feel apply.	Yes 	No 
Will taking part in the research put participants under any particular burden and/or risk? If yes, describe how this will be mitigated.		
	Yes 	No 
The study will involve phlebotomy. Common risks associated with phlebotomy are pain during the procedure and bruising with associated pain afterwards. Less common risks include dizziness and the potential for fainting during the procedure. To minimise these risks, the staff undertaking the procedure will be fully trained in phlebotomy. Bruising after the event will also be reduced by promptly applying pressure on the puncture site		

after the needle is withdrawn. All participants will be fully informed about these risks in the Participant Information Sheet.

There is a theoretical risk that a participant may have an adverse reaction to the study drug. Participants will be informed of the potential side-effects prior to taking the medication. To minimise risk, the participants' general health will be assessed before being accepted into the study. They will be excluded from the study if they are currently taking any regular medications (except the contraceptive pill) or if they have any known contraindications to taking the drug (see exclusion criteria).

Statins are considered extremely safe drugs: their more common side-effect are muscle pain or weakness (usually mild and quickly responding to stopping or switching medication) and elevation of liver transaminases (significant only in case of pre-existing hepatic disease), whereas more serious adverse events include rhabdomyolysis (very rare but severe myopathy associated with elevated creatine kinase and myoglobinuria), new-onset diabetes mellitus (in predisposed individual with pre-existing hyperglycaemia), and haemorrhagic stroke (in patients with prior haemorrhagic stroke or lacunar infarct); however, clinical trials have ultimately concluded that such adverse events attributed to statin therapy in routine practice are not actually caused by it (Collins-2016), especially at doses lower than 80mg/day and when used for less than 52 weeks (Li-2016). Other common ($\geq 1/100$, $< 1/10$) but usually mild side-effects include: nasopharyngitis, pharyngo-laryngeal pain, epistaxis, headache, and gastrointestinal disturbances (constipation, diarrhoea, flatulence, dyspepsia, nausea). The potential side-effects and adverse events will be clearly stated in the Participant Information Sheet and researchers will discuss these with participants as part of the informed consent procedure.

To minimise the risk associated with side-effects, participants will be contacted on days 2 and 4 of the study week by a named researcher to check there are no concerns. All participants will have 24-hour contact details of a named researcher who they can contact during the study period. The named researcher will in turn contact a qualified medical doctor if necessary. In order to limit the risks associated with fatigue, during the week of statin/placebo administration, participants will be advised not to drink alcohol, and not to carry out activities requiring full alertness if they are aware of any impairment.

If judged necessary by the medical lead, the randomisation code will be broken for that individual by the medical supervisor and the participant will be advised to stop taking the medication and withdrawn from the study.

Will the research involve deliberate deception of participants?
 
If yes, justify why deception is used, describe deception and debriefing process, and include debriefing documents in the application
	Yes 	No 
---	------------------------------	--


Will any procedures affect your own physical and/or psychological safety as a researcher?
 
If yes, describe how this will be mitigated.
	Yes 	No 
--	------------------------------	--

Does your research raise issues relevant to the Counter-Terrorism and Security Act (the Prevent Duty), which seeks to prevent people from being drawn into terrorism?
 
If yes, please say how you plan to address any related risks. Please see advice on this on our Best Practice Guidance Web Page.
	Yes 	No 
---	------------------------------	--

Please give details of any other ethical and/or safety considerations

None

